17.8.4. SIMPSON-ANGUS SCALE (SAS)

The SAS is a clinician-rated assessment of neuroleptic-induced Parkinsonism consisting of 10 items. Items are anchor-based, rated on a 5-point scale (ranging between 0 and 4), and address rigidity, gait (bradykinesia), tremor, akathisia, shoulder shaking, glabellar tap, and salivation.

SAS mean score is defined as the average of all 10 items and ranges between 0 and 4. Lower values of the SAS mean score indicate milder symptoms. If one or more of the SAS items are missing at a visit, the SAS mean score will be set to missing for that visit.

The SAS mean score at each visit will be classified as 'abnormal' if it exceeds 0.3 (Rush, et al., 2000). Otherwise, the non-missing SAS mean score will be classified as 'normal'.

SAS is assessed at these study visits: Visit 2 and Visit 10.

The observed SAS mean score and the change from Baseline values will also be summarized descriptively by treatment group and visit. In addition, the observed SAS mean score and the change from Baseline values will be summarized descriptively by the subgroups of concomitant medication use for treatment of movement disorders.

Document: PPD

Author: PPD

Version Number:

1.0

Version Date:

06MAY2024

Shift from Baseline in SAS mean score category (Normal/Abnormal) to each post-Baseline scheduled visit (Week 8/Visit 10) and to the overall post-Baseline period (including both the treatment period and the follow-up period) will be summarized descriptively by treatment group.

17.8.5. PITTSBURGH SLEEP QUALITY INDEX

The Pittsburgh Sleep Quality Index (PSQI) consists of 19 self-rated questions and 5 questions rated by the bed partner or roommate (if one is available). It is used to measure the quality and patterns of sleep in adults. Only self-rated questions are included in the scoring. It differentiates “poor” from “good” sleep quality by measuring seven “component” scores, each of which has a range of 0-3 points: subjective sleep quality, sleep latency, sleep duration, habitual sleep efficiency, sleep disturbances, use of sleeping medications, and daytime dysfunction due to sleepiness over the last month.

The seven component scores are then summed to yield one global PSQI score, with a range of 0-21 points, “0” indicating no difficulty and “21” indicating severe difficulties in all areas ([Buysse, Reynolds, Monk, Berman, & Kupfer, 1989](#)).

The PSQI scoring algorithm as downloaded from the University of Pittsburgh Sleep and Chronobiology Center is inserted in [APPENDIX 8](#). The seven component scores and the PSQI global score will be derived according to this algorithm. If one or more of the component scores are missing at a visit, the PSQI global score will be set to missing for that visit.

PSQI is assessed at these study visits: Visit 2, Visit 6 and Visit 10.

The observed PSQI global score and the change from Baseline values will be summarized descriptively by treatment group and visit.

17.9. SUBGROUP ANALYSIS OF SAFETY VARIABLE(S)

The subgroup analyses for AE data, vital signs data, and AIMS/BARS/SAS scales are described in their respective sections.

18. PHARMACOKINETIC ANALYSIS

Plasma concentrations of SEP-363856 and SEP-363854 (metabolite of SEP-363856) of all enrolled subjects will be presented in a data listing.

Document:

PPD

Author:

PPD

Version Number:

1.0

Version Date:

06MAY2024

19. DATA NOT SUMMARIZED OR PRESENTED

The variables and/or domains not summarized or presented are:

- Subject initials
- Any data collected on screen failures other than disposition, basic demographics, and pre-treatment events.
- Any data collected during previously failed screening(s) for randomized subjects who were screened more than once except Adverse Events.

These domains and/or variables will not be summarized or presented but will be available in the clinical study database and SDTM datasets.

APPENDIX 1. PROGRAMMING CONVENTIONS FOR OUTPUTS

IQVIA OUTPUT CONVENTIONS

The following output conventions are to be followed:

- General presentation:
 - The first row in the body of the table or listing should be blank
 - Rounding should be done with the SAS function ROUND.
 - Numbers in tables should be rounded, not truncated.
 - The first letter of a text entry should be capitalized.
- Univariate Statistics: If the raw data has N decimal places, then the summary statistics should have the following decimal places:
 - Minimum and maximum: N
 - Mean, median, Q1, and Q3: N + 1
 - SD: N + 2
 - For lab data only, in the rare case where raw data has more than 3 decimal places, summary statistics will be presented for the scenario of N = 3. All decimals will be presented in Listings.
 - For CGI-S score, 2 decimal places will be presented for mean, median, Q1, Q3, LS mean, LS mean difference, and 95% CI; 3 decimal places will be presented for SD and SE; 0 decimal places will be presented for min and max. 0 decimal places will be presented in listings.
 - For UPSM scores, 3 decimal places will be presented for mean, median, Q1, Q3, LS mean, LS mean difference, and 95% CI; 4 decimal places will be presented for SD and SE; 2 decimal places will be presented for min and max. Up to 2 decimal places will be presented in Listings. No rounding will be applied in the ADaM datasets.
- Frequencies and percentages (n and %):
 - Percentages will be reported to one decimal place, except cases where percent <100.0% but >99.9% will be presented as '99.9%' (e.g., 99.99% is presented as >99.9%); and cases where percent < 0.1% will be presented as '<0.1%' (e.g., 0.08% is presented as <0.1%). Rounding will be applied after the <0.1% and >99.9% rule.
 - Where counts are zero, no percentage should appear in the output.
- Confidence Intervals:

Document: PPD

Author: PPD

Version Number:

1.0

Version Date:

06MAY2024

- o Confidence intervals and estimates are presented to one place more than the raw data, and standard errors to two places more than the raw data.
- o Boundary values of confidence intervals should be separated by a comma.
- P-values should be reported to three decimal places, except values <1.000 but >0.999 will be presented as '>0.999' (e.g., 0.9998 is presented as >0.999); and values <0.001 will be presented as '<0.001' (e.g., 0.0009 is presented as <0.001). Rounding will be applied after the <0.001 and >0.999 rule.
- Ratios should be reported to one more decimal place than the raw data.
- Missing values:
 - o A "0" should be used to indicate a zero frequency.
 - o A “-” will be used to indicate missing data in an end-of-text table or subject listing.
 - o

DATES & TIMES

Depending on data available, dates and times will take the form yyyy-mm-ddThh:mm:ss .

SPELLING FORMAT

English US.

PRESENTATION OF TREATMENT GROUPS

For outputs, treatment groups will be represented as follows and in that order:

Treatment Group	For Tables (Column Order)	For Listings and Graphs (Order)
SEP-363856 50 to 100 mg/day	SEP-363856 50 to 100 mg/day	SEP-363856 50 to 100 mg/day

Document: PPD

Author: PPD

Version Number:

1.0

Version Date:

06MAY2024

LISTINGS

All listings will be ordered by the following (unless otherwise indicated in the template):

- Enrolled subjects who did not receive any study medication will be presented at the end and labelled “Not Treated”.
- Subject ID.
- Visit (where applicable)
- Original date/time (where applicable).

Document:

PPD

Author:

PPD

Version Number:

1.0

Version Date:

06MAY2024

APPENDIX 2. PARTIAL DATE CONVENTIONS

The actual dates as collected on the CRF will be presented in the listings. Imputed dates will not be presented in the listings unless otherwise specified.

ALGORITHM FOR ADVERSE EVENTS

As a general rule, if the start date of an AE is available and the start time of the AE is not available, the AE will be considered to have started after the study drug dose administered on the day of the AE start date.

In case of partial or missing AE start and/or end dates, impute partial or missing event start and/or end dates (if not ongoing) using the algorithm below. If an AE has some missing components in both the start and end dates, first impute the end date.

AE end date imputation

- If year and month (YYYY-MM) of AE end date are known, then impute the missing day to be the earlier of (last day of the month; date of last contact).
- If only year (YYYY) of AE end date is known, then impute the missing month and day to be the earlier of (31st December; date of last contact).
- If AE end date is completely missing and AE is not ongoing, then impute AE end date to be date of last contact.

AE start date imputation

- If year and month (YYYY-MM) of AE start date are known and YYYY-MM = year and month of 361-30 study med start date, then impute AE start date to be the earlier of (361-308 study med start date; full or imputed AE end date [if non-missing]).
- If year and month (YYYY-MM) of AE start date are known and YYYY-MM ≠ year and month of 361-308 study med start date, then impute AE start date to be YYYY-MM-01.
- If only year (YYYY) of AE start date is known and YYYY = year of 361-308 study med start date, then impute AE start date to be the earlier of (361-308 study med start date; full or imputed AE end date [if non-missing]).
- If only year (YYYY) of AE start date is known and YYYY ≠ year of 361-308 study med start date, then impute AE start date to be YYYY-01-01.

Document: PPD

Author: PPD

Version Number:

1.0

Version Date:

06MAY2024

- If AE start date is completely missing, then impute AE start date to be the earlier of (361-308 study med start date; full or imputed AE end date [if non-missing]).

Using the full or imputed event dates, assign events into pre-treatment events vs. AE as described below.

If both event start date/time and 361-308 study med start date/time are available:

- If event start date/time < 361-308 study med start date/time, then pre-treatment event.
- If event start date/time \geq 361-308 study med start date/time, then AE.

If (event start date is available and time is not available) and/or (361-308 study med start date is available and time is not available):

- If event start date < 361-308 study med start date, then pre-treatment event.
- If event start date \geq 361-308 study med start date, then AE.

Document: PPD

Author: PPD

Version Number:

1.0

Version Date:

06MAY2024

ALGORITHM FOR PRIOR / CONCOMITANT / POST-TREATMENT MEDICATIONS

In case of partial or missing medication start and/or stop dates, impute the partial or missing dates using the algorithm below.

If a medication has some missing components in both the start and stop dates, first impute the stop date.

Impute stop date as latest possible date

- If only day unknown, impute to the earlier of (last day of the month; date of 361-308 last contact).
- If month and day unknown, impute to the earlier of (31st December; date of 361-308 last contact).
- If stop date is completely unknown and medication is not ongoing, impute to date of 361-308 last contact.

Impute start date as earliest possible date

CRF questions: 'Started prior to first dose?' = Yes; 'Started after last dose of study medication?' = No.

- If only day unknown, impute to the later of (first day of the month; date of birth [if full date is available]).
- If month and day unknown, impute to the later of (1st January; date of birth [if full date is available]).
- If start date is completely unknown, impute to the earlier of (date of informed consent*; full or imputed medication stop date [if not missing]).

CRF questions: 'Started prior to first dose?' = No; 'Started after last dose of study medication?' = Yes.

- If only day unknown, impute to the later of (first day of the month; 361-308 study med end date + 1).
- If month and day unknown, impute to the later of (1st January; 361-308 study med end date + 1).
- If start date is completely unknown, impute to 361-308 study med end date + 1.

CRF questions: 'Started prior to first dose?' = No; 'Started after last dose of study medication?' = No.

- If only day unknown, impute to the later of (first day of the month; 361-308 study med start date).
- If month and day unknown, impute to the later of (1st January; 361-308 study med start date).
- If start date is completely unknown, impute to 361-308 study med start date.

Document: PPD

Author: PPD

Version Number:

1.0

Version Date:

06MAY2024

Then assign a medication into prior, concomitant, or post-treatment

The concept of “date” below should also include time information whenever time is available for both comparators.

- If medication stop date < 361-308 study med start date, assign as prior.
- If (medication stop date \geq 361-308 study med start date or medication is ongoing) and medication start date \leq 361-308 study med end date, assign as concomitant.
- If medication start date > 361-308 study med end date, assign as post-treatment.

Overriding rule

For the case where the medication start date is known and is equal to 361-308 study med end date and the medication start time is unknown, or the case where the imputed medication start date is equal to 361-308 study med end date:

- If CRF question ‘Started after last dose of study medication?’ = No, then assign as concomitant.
- If CRF question ‘Started after last dose of study medication?’ = Yes, then assign as post-treatment.

Document:

PPD

Author:

PPD

Version Number:

1.0

Version Date:

06MAY2024

PARTIAL DATE IMPUTATION RULES FOR INITIAL ONSET OF SCHIZOPHRENIA

For subjects with partial onset date of schizophrenia, impute the onset date using the following rules:

- If only day unknown, impute as the earlier of: 15th of the month, or date of ICF*.
- If both month and day unknown, impute as the earlier of: June 30th of the year, or date of ICF*.

*For adolescent subjects, the later of the ICF date and IAF date should be used.

PARTIAL DATE IMPUTATION RULES FOR CURRENT ONSET OF ACUTE EXACERBATION

For subjects with partial onset date of acute exacerbation, impute the onset date using the following rules:

- If only day unknown and the known year and month is earlier than the year and month of ICF*, impute as the later of: 15th of the month, or date of initial onset of schizophrenia (actual or imputed).
- If only day unknown and the known year and month is the same as the year and month of ICF*, impute as the later of: earlier of (date of ICF*, 15th of the month), or date of initial onset of schizophrenia (actual or imputed).
- If both month and day unknown and the known year is earlier than the year of ICF*, impute as the later of: June 30th of the year, or date of initial onset of schizophrenia (actual or imputed).
- If both month and day unknown and the known year is the same as the year of ICF*, impute as the later of: earlier of (date of ICF*, June 30th of the year), or date of initial onset of schizophrenia (actual or imputed).

*For adolescent subjects, the later of the ICF date and IAF date should be used.

PARTIAL DATE IMPUTATION RULES FOR FIRST HOSPITALIZATION

For subjects with partial date of first hospitalization for treatment of schizophrenia, impute the date using the following rules:

- If only day unknown, impute as the earlier of: 15th of the month, or date of ICF*.

Document: PPD

Author: PPD

Version Number:

1.0

Version Date:

06MAY2024

- If both month and day unknown, impute as the earlier of: June 30th of the year, or date of ICF*.

*For adolescent subjects, the later of the ICF date and IAF date should be used.

For subjects whose date of first hospitalization for treatment of schizophrenia is completely missing AND the number of prior hospitalizations for treatment of schizophrenia is 0, impute the date of first hospitalization to be the *"Date of admission for this study hospitalization"* collected on the *"Psychiatric Hospitalization (HOSP)"* CRF form.

PARTIAL DATE IMPUTATION RULES FOR FIRST ANTI-PSYCHOTIC DRUG THERAPY

For subjects with partial start date for the first anti-psychotic drug therapy of at least 2 weeks duration intended for treatment of schizophrenia, impute the start date using the following rules:

- If only day unknown, impute as the earlier of: 15th of the month, or date of ICF*.
- If both month and day unknown, impute as the earlier of: June 30th of the year, or date of ICF*.

PARTIAL DATE IMPUTATION RULES FOR ONSET OF INITIAL BEHAVIORAL DISTURBANCE

For adolescent subjects with partial onset date of initial behavioral disturbance, impute the onset date using the following rules:

- If only day unknown, impute as the earlier of: 15th of the month, or the later of (date of ICF and date of IAF).
- If both month and day unknown, impute as the earlier of: June 30th of the year, or the later of (date of ICF and date of IAF).

Document:

PPD

Author:

PPD

Version Number:

1.0

Version Date:

06MAY2024

RULES FOR ASSIGNING DOSEON/DOSEA

- In general, DOSEON/DOSEA should be the dose level immediately before the start of an AE or an assessment. In case the AE or the assessment start date/time coincides with the first dosing start date/time of the study, the DOSEON/DOSEA should be assigned to the dose level associated with that first dosing start date/time. In case the AE or the assessment start date/time coincides with a dosing start date/time other than the first dosing start date/time, the DOSEON/DOSEA should be assigned to the dose level associated with the previous dosing start date/time.
- In case of missing AE start time, missing assessment (start) time, and/or missing dosing start time, DOSEON/DOSEA should be assigned using the algorithm in the table below.

Scenario	Data	Rules
Dosing start date and start time both available	Adverse Events	If AE start date is available and AE start time is missing, dose on the same day as AE start should be assigned as DOSEON.
	Scales/Questionnaires, Vitals, Labs, ECG	If assessment start date is available and assessment start time is missing, dose on the previous day of the assessment should be assigned as DOSEA.
Dosing start date available but start time missing	Adverse Events	Regardless of whether AE start time is available, dose on the same day as AE start should be assigned as DOSEON.
	Scales/Questionnaires, Vitals, Labs, ECG	Regardless of whether assessment start time is available, dose on the previous day of the assessment should be assigned as DOSEA.

- In case of partial or missing AE start date, the imputed AE start date will be used for the purpose of assigning DOSEON.

Document: PPD

Author: PPD

Version Number:

1.0

Version Date:

06MAY2024

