Informed consent will be obtained from each subject before any study procedures are performed. Subjects will be evaluated for eligibility during a Screening Period of up to 21 days, during which they will continue on their pre-switch antipsychotic medication while being tapered off any prohibited medications ([Section 10.3.2](#)) in a manner that is consistent with labeling recommendations and conventional medical practices. Non-prohibited psychotropic medications other than the pre-switch antipsychotic may be continued during the study but must have been stable for at least 6 weeks prior to Screening and should be maintained at a stable dose and regimen (see [Section 10.3.1](#)).

Subjects who are being treated with two antipsychotic medications will be permitted to enter the Screening Period. At the start of Screening, the Investigator will determine which antipsychotic medication is considered “primary”, and the other one will be tapered off during the Screening Period.

Subjects who screen fail may be re-screened twice, if judged appropriate by the Investigator after discussion with the Medical Monitor. Re-screened subjects will be re-consented, assigned a new subject number, and all Visit 1 procedures will be repeated.

Open-label Treatment Period (8 weeks):

At Baseline (Day 1) (pre-switch [PS] Baseline), subjects who have successfully completed Screening and have met the eligibility criteria will begin open-label treatment with SEP-363856 while continuing to take the full dose of their pre-switch antipsychotic. SEP-363856 dosing will begin the evening of the PS Baseline visit and will continue once-daily, in the evening at bedtime, for the remainder of the Treatment Period, during which the procedures outlined in [Table 2](#) will be conducted. Subjects will be evaluated at PS Baseline and weekly throughout the rest of the study. [Section 10.3](#) describes the circumstances and specifications for which prior and concomitant psychotropic medications other than the pre-switch antipsychotic are allowed in this study.

Subjects will receive SEP-363856 50 mg/day from Day 1 through Day 3 and 75 mg/day from Day 4 through Day 7. Every effort should be made to maintain subjects at 75 mg/day from Day 4 through Day 7. Beginning on Day 8, the dose of SEP-363856 can be adjusted in increments of 25 mg among 3 dose levels (50, 75 and 100 mg), according to the following requirements:

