17.3.1. ALL AEs

All AEs will be summarized by PT, by SOC and PT, as well as by SOC, HLT, and PT. The summary by SOC and PT will also be presented for the following subgroups: sex, age group and BMI category.

Summary tables (by SOC and PT) will be generated for those AEs starting after the last dose of study drug and those AEs starting more than 1 day after the last dose of study drug.

AEs reported by $\geq 2.0\%$ (without rounding) of subjects in any treatment group will be summarized by SOC and PT.

Non-serious AEs reported by $> 5.0\%$ (without rounding) of subjects will be summarized by SOC and PT.

The summary by SOC and PT will be broken down further by maximum severity and by strongest relationship to study medication. These summaries are described in the sections below.

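### For adverse events with a missing AE or dosing time, SAP Appendix 2 assigns the same-day dose although the drug is taken at bedtime, which misstates dose at onset on dose-change days and puts untimed last-dose-day events into the after-last-dose tables

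*SAP*

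**What the plan says.** Protocol 7.1 fixes the time of dosing: "SEP-363856 dosing will begin the evening of the PS Baseline visit and will continue once-daily, in the evening at bedtime".

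SAP Appendix 2, in the algorithm for adverse events, deals with an AE that has a start date but no start time: "the AE will be considered to have started after the study drug dose administered on the day of the AE start date".

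The DOSEON/DOSEA rules later in that appendix open with a principle: "In general, DOSEON/DOSEA should be the dose level immediately before the start of an AE or an assessment". If an onset coincides with a dosing start other than the first, the earlier dose level is used. A table then covers missing times:

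- AE time missing, dosing time known: "If AE start date is available and AE start time is missing, dose on the same day as AE start should be assigned as DOSEON".
- Dosing time missing: "Regardless of whether AE start time is available, dose on the same day as AE start should be assigned as DOSEON".
- Scales, vital signs, laboratory tests and ECGs, dosing time missing: "Regardless of whether assessment start time is available, dose on the previous day of the assessment should be assigned as DOSEA". The previous day's dose is also used when only the assessment time is missing.

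SAP 17.3.1 plans two separate tables, covering "those AEs starting after the last dose of study drug and those AEs starting more than 1 day after the last dose of study drug". Protocol 15.3.5.2 also plans a separate summary of AEs that start after the last dose, up to 9 days. SAP 17.3.7 plans a table of serious AEs in the 7 days after the last dose.

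**The concern.** The missing-time rules for AEs fit morning dosing. With a bedtime dose, an AE noticed during the day precedes that day's tablet, and the dose in effect is the one taken the evening before. An AE that begins after midnight, a few hours after a dose, carries the next date and is attributed to a tablet still about a day away.

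Two things are at stake. The first is dose at onset on the days when it is informative. An untimed AE on the day of a dose increase is labelled with the higher level before it was taken, and an untimed AE that prompts a same-day reduction is labelled with the lower level. The second is the after-last-dose tables, which would take in untimed events from the last dosing date, many of which probably began before that evening's dose.

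**Working it through.** The plan gives no figure to reproduce here, so the check traces the rules.

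**Inputs.** Evening dosing from Day 1, 50 mg on Days 1–3, 75 mg on Days 4–7 and an increase to 100 mg on Day 8 if tolerated (Protocol 7.1). Dosing times recorded for the initial and final administration of each visit (Protocol 10.2). Treatment taken as 56 evening doses. The documents give no clock time for bedtime; 20:00 to 24:00 is assumed.

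**Step 1: order within the day.** The share of the calendar day before the dose is bedtime/24: 20/24 = 83%, 22/24 = 92%, 24/24 = 100%. This is a share of the clock. It is neither a share of events nor an error rate.

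**Step 2: when the level is wrong.** DOSEON is a dose level, so same-day and previous-day assignment differ only where the level changes.

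| Day of untimed daytime AE | Level assigned by Appendix 2 | Level last taken |
|---|---|---|
| Day 4 | 75 mg | 50 mg |
| Day 8 | 100 mg | 75 mg |
| All other days from Day 2, default titration | same | same |

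Share of days affected: 2/56 = 3.6%. If onsets were spread evenly over days and hours, the share of untimed AEs with a wrong level would be between 2/56 × 20/24 = 3.0% and 2/56 × 24/24 = 3.6%. If the level changed on Day 4 and at all six weekly visits from Day 8 to Day 43, the share of days would be 7/56 = 12.5%, before any unscheduled change. Onsets may cluster around titration, in which case the share of events would be larger.

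**Step 3: the branch that discards a known AE time.** If an AE is recorded at 09:00 on Day 8 and the dosing time is missing, Appendix 2 still assigns 100 mg. The level immediately before onset, which its own principle asks for, is 75 mg. The Day 4 step falls between Visits 2 and 3, so on a literal reading of Protocol 10.2 its dosing time may not be collected. That is an inference, because the case report form is not available.

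**Step 4: the last-dose date.** An untimed AE on that date is deemed to start after that day's dose, which is the last dose. It therefore enters the first table of SAP 17.3.1, the separate summary of Protocol 15.3.5.2 and, if serious, the table of SAP 17.3.7. It does not enter the table of AEs more than 1 day after the last dose. It remains in the main AE summary, which under Protocol 15.3.5.2 runs from the first dose to 9 days after the last.

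**Step 5: medications compared.** For a medication that starts on the last-dose date with no time, Appendix 2 settles the order with a case report form question on whether it started after the last dose. It gives no such rule for AEs.

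**The case against.** The strongest reply is that the untimed branch is internally consistent. Once an AE is deemed to follow that day's dose, the same-day level is the level immediately before onset. The opening principle is also worded as a general rule, with the table supplying exceptions. This stands for the untimed branch, where the fault lies in the premise, which suits bedtime dosing poorly. It does not rescue the branch that ignores a recorded AE time.

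It can also be said that assessments happen at daytime visits, so the previous-day rule is safe for them, whereas an AE can start at any hour. That is fair. It still leaves the previous evening's dose as the better default when the hour is unknown.

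The SAP's worst-case reasoning (SAP 17.3) concerns AE versus pre-treatment event. It justifies the Day 1 convention and gives no reason for later days or the last day.

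A reader might infer three stronger things that the documents do not support:

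- *Last-day AEs are reclassified as post-treatment.* SAP 17.3 has no such class for AEs. The events stay in the main summary, and because the more-than-1-day table leaves them out, comparing the two tables partly isolates them.
- *The rule is wrong for most untimed events.* It often points to a dose not yet taken, but the level is the same on days without a dose change.
- *The after-last-dose table would be read as withdrawal or rebound.* Nothing gives it that purpose. SAP Appendix 5 says drug withdrawal is evaluated as its own concept with a dedicated MedDRA query.

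**Conclusion.** The point holds, with bounded effect. The AE missing-time rules do not fit bedtime dosing, differ from the assessment rule beside them and, in one branch, override a known AE time.

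Two effects follow. The dose level at onset is wrong on dose-change days, and untimed last-dose-day AEs enter the after-last-dose tables. The first is confined to dose at onset in the data: the documents specify no summary by DOSEON, and Protocol 15.3.5.2 summarises AEs by modal daily dose. The second reaches planned tables but removes nothing from the main AE summary. The primary and secondary discontinuation endpoints are untouched.

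The day counts assume the default titration and 56 doses. The number of records affected cannot be estimated, because the documents give no rate of missing AE or dosing times.

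**What to change.** Amend SAP Appendix 2 as follows.

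1. From Day 2, if the AE start time is missing, set DOSEON to the previous day's dose, as DOSEA already does. If only the dosing time is missing, compare the recorded AE time with the protocol's bedtime dosing, so that a daytime onset takes the previous day's dose. Where the order cannot be settled, for example an onset close to bedtime, default to the previous day's dose. A blanket previous-day rule would not do, because it too would ignore a recorded AE time.
2. State that an AE on the last-dose date with no start time is not counted as starting after the last dose.
3. Keep the worst-case rule that untimed Day 1 events are AEs, with DOSEON set to the first dose.

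The cost is a few lines in Appendix 2 and a small programming change. No new data are needed.
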